### **3.0 Study Endpoints/Events/Outcomes**

- 3.1 Primary Endpoint/Event/Outcome:  
Neural activity in vmPFC, insula, amygdala, and hypothalamus; salivary cortisol, heart rate, and respiration
- 3.2 Secondary Endpoint(s)/Event(s)/Outcome(s):  
Exploration of possible sex differences in different conditions later in puberty but not earlier in puberty.

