#### Parent:

- Required safety screening questionnaire to confirm child's safety in the MRI scanner
- *[If the child is randomized to the parent-present buffering condition],* sit in a separate room while connected via video conference call to research staff in the MRI console room for duration of MRI scan (approx. 1 hour)

Child:

- Required safety screening questionnaire to confirm child's safety in the MRI scanner
- Saliva sampling at 10 time points throughout the testing session to assess levels of stress-sensitive compounds, including cortisol, alpha amylase, and DHEA.
- Children chew on an absorbent sponge for 1-2 minutes to acquire each saliva sample.
- Measure height and weight using a stadiometer.
- Practice in a pretend MRI machine to gain familiarity with the scanning environment and assess comfort in the scanner bore (i.e., rule out claustrophobia)
- Standard non-invasive structural and functional MRI scanning for 1 hour at 3-Tesla (clinical standard) field strength.
- Collection of physiological data during the MRI scan (respiration belt, and pulse oximeter and/or 3 EKG leads).
- Performance of a social evaluative stress test during MRI scanning.  
(1) Five minutes of silent preparation of a speech about oneself, (2) Oral delivery of the speech to two judges in white lab coats, visible by video feed via video conference call, and (3) Performance of challenging, but age-appropriate math problems under timed limited conditions, while observed by the same two judges. To increase the social evaluative component of the stress, youth are told that we will be video recording their speech and will show it to a panel of kids their age who will rate their performance. Although, we do video record, we will not show anyone the child's performance. The social evaluative stress created by this test depends upon both the visible judges and the belief of a recording that is shown to peers. Without one of these aspects, the stress test does not reliably produce a stress response in the studied population. The research goals of this study cannot be met without a reliable and standard social evaluative stress test. This is standard practice of the Trier Social Stress Test. This recording will be used for training and data purposes only.
- Completion of a post-scan survey to assess perceived stress at various points throughout the session.

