### **Physiological Measures.**

**Stress Hormones:** We will assay saliva samples for stress sensitive hormones: cortisol and alpha-amylase. Saliva will be collected using SalivaBio Oral Swabs (SOS) or passive drool and stored frozen at -20°C until shipped for assay. All testing will be conducted in the late afternoon to control for circadian rhythm. Medications will be recorded from parent report and classes of drug codes will be used to group meds by presumed mechanisms of action and will be entered as covariates (Granger et al., 2009). Systemic glucocorticoid medications are an exclusion criterion. For each analyte, we will calculate area under the curve from intercept (AUCi) to provide a single measure for the main analysis.

**Pubertal Hormones - DHEA, Testosterone, Estradiol:** Sufficient saliva will be obtained at sampling to assay for these additional pubertal hormones. These assays will be performed if we obtain a sex by condition by pubertal development (3-way) interaction on key outcome measures. If so, these measures may provide insight into the mechanism of these interactions ([Butler et al., 1989](#); [Mehta, Mor, Yap, & Prasad, 2015](#)).

**Physiological Recording:** Participants will wear standard Siemens physiological recording equipment for the MRI environment (respiration belt, and pulse oximeter or EKG leads). Samples will be collected throughout the entire MRI scan. Response measures will be computed by regressing the stress condition values on comparison condition values and saving the residual as the response measure.

All questionnaires and surveys are included in the ETHOS portal. Contact information and child age will be obtained from an existing registry of families who have expressed interest in child development research (specifically, parent name(s), address, phone number, email address, child

**PROTOCOL TITLE:** An MRI Study of Stress and Social Support

**VERSION DATE:** v.5.5 2022.09.20

name, child sex, and child birthdate). All other data will be acquired directly from the participants, and information obtained from the participant registry will be verified verbally with the parent.

**5.3 Study Duration:** Participants will attend two sessions. Each session will last approximately 2 hours.

- All participants will be enrolled and assessed within a 30-month period.
- Primary data analysis endpoints will be available within 1 year of the end of data collection (i.e., 42 months from initial enrollment).

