## 15.0 Statistical Considerations

*15.1 Data Analysis Plan:*

Preliminary Analyses to Determine Covariates Needed for Primary Analyses. The purpose of collecting data on potential covariates is to identify variables that are correlated with both the independent variable (social buffering condition, sex, pubertal stage) and the primary outcome measures. Those covariates that are associated with the independent and outcome variables will be controlled for in the primary analyses. Those that are not will be used to describe the sample, but will not need to be included in the analyses to obtain unbiased estimates. For each potential covariate, we will conduct correlations or t-tests with pubertal stage, and t-tests, ANOVAs, or chi-square tests (as appropriate) with sex and condition. If data do not confirm to modeling assumptions, we will use nonparametric analogs instead.

Preliminary Analyses of Imaging Data to Yield Primary Outcome Measures: fMRI data will be analyzed in FSL software (version 5.0.10) to generate voxel-wise contrast maps. Mean signal values will be extracted from these maps in a priori regions of interest for every participant using the methods described below. These preliminary analyses are used to generate the fMRI outcome variables of interest. The values of these outcome variables for each participant will be used in the general statistical analyses described in the next section. In total, these preliminary analyses will yield 6 primary task-related outcome variables, and 6 primary connectivity-related outcome variables.

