### 15.3 Statistical Analysis of MRI and non-MRI Outcome Variables:

The following is a list of the analyses that we will perform on the outcome measures. They are classified as to whether they are the primary or mediational analyses. All statistical analyses will be performed in R.

The primary analyses will consist of a series of multiple regression models. For each dependent variable, variation in neural activity, cortisol response, and heart rate response, we will begin by testing the three-way interaction between social buffering condition, sex, and pubertal stage for all outcomes. If the three-way interaction is not significant, we will then examine all two-way interactions. If the two-way interactions are not significant, we will then examine main effects only models. If the three-way interaction is significant, we will not examine any other model. If condition is significant as an interaction or as a main effect, we will examine all pairwise comparisons using Tukey's Honestly Significant Difference test.

Multiplicity of testing. We will correct for multiple comparisons using the Benjamini-Hochberg (BH) correction. The BH method works by controlling the false discovery rate, and relative to the Bonferroni's correction is more powerful, while still adequately protecting against Type I error (Williams, Jones, & Tukey, 1999).

Mediational Analysis. When changes in activity of brain regions differ by condition or condition by pubertal status and we also see condition or condition by pubertal status differences for cortisol, or heart rate, then we will examine whether brain activity differences mediate the neuroendocrine or autonomic differences. This will be examined using path analysis, while controlling for covariates identified in the preliminary

covariate analysis, and will be estimated using the lavaan package in R (Rosseel, 2012).

The significance of all indirect effects will be assessed using bias-corrected 95% confidence intervals (Efron & Tibshirani, 1986), where confidence intervals that are non-overlapping with zero will be considered significant.

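### Heart-rate and respiration responses are built as saved residuals and then regressed on condition, sex and puberty, which can distort, usually toward zero, the effect of any predictor related to the comparison value

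*Combined protocol and SAP*

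**What the plan says.** Section 3.1 lists the primary outcomes as "Neural activity in vmPFC, insula, amygdala, and hypothalamus; salivary cortisol, heart rate, and respiration".

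For the autonomic signals, Physiological Measures (section 5.2) says that response measures are computed by "regressing the stress condition values on comparison condition values and saving the residual as the response measure". It does not say which scan segment supplies the comparison values, and it does not put condition, sex or pubertal stage into that regression.

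Section 15.3 sets out the second stage: "For each dependent variable, variation in neural activity, cortisol response, and heart rate response" are the outcomes, and "we will begin by testing the three-way interaction between social buffering condition, sex, and pubertal stage for all outcomes". Two-way and then main-effects models follow if the higher-order terms are not significant. The comparison value is not a term in these models. Respiration is not named there, although it is primary in section 3.1.

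Section 15.1 gives the covariate rule: "Those covariates that are associated with the independent and outcome variables will be controlled for in the primary analyses".

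On timing, section 5.1 (Visit 2, Parent) says that in the parent condition the parent is linked by video call to staff "in the MRI console room for duration of MRI scan (approx. 1 hour".

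**The concern.** A residual saved from a regression that omits the study predictors is not the same as adjusting for the comparison value. The first step credits to the comparison value whatever part of a predictor's effect runs along with it. The second step cannot recover that part, because the comparison value is no longer in the model.

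The covariate screen in section 15.1 would not repair this. A saved residual is uncorrelated with the comparison value by construction, so the comparison value cannot show the association with the outcome that the screen requires.

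Puberty and sex are observed rather than randomised, so nothing in the design makes them independent of a child's heart rate or respiration in the comparison period. Randomisation protects condition only if the comparison value is recorded before condition can act on it, and the plan does not establish that. At stake are the estimates for heart rate and, if it is handled the same way, respiration.

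**Working it through.** **The plan's own figure.** Section 15.2 gives a minimum detectable f² of 0.056 at N = 200 and .070 at N = 160 for the three-way term (alpha .05, power .80, 12 covariates). With three conditions the model has 12 covariates + 4 main-effect + 5 two-way + 2 three-way = 23 terms, so u = 2 and v = 200 − 23 − 1 = 176 (136 at N = 160). The noncentral F with λ = f²(u + v + 1) gives 0.0548 and 0.0709. Power at the stated values is 0.809 and 0.795. The figures are reproduced closely and do not depend on the residual step.

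**One predictor.** Let the stress value be Y = βB + bX + e, with comparison value B, predictor X and r = corr(X, B), all centred.
- Step one regresses Y on B alone. Its slope is β + b·r·(σX/σB), not β.
- The saved residual is therefore bX − b·r·(σX/σB)·B + e.
- Regressing this on X gives b − b·r² = b(1 − r²).
- The test statistic falls by about √(1 − r²). A test with 80% power under single-model adjustment has power Φ[(1.960 + 0.842)√(1 − r²) − 1.960] under the residual method.

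| Assumed r | Coefficient kept | Power (from 80%) |
|---|---|---|
| .1 | 99% | 79.6% |
| .2 | 96% | 78.4% |
| .3 | 91% | 76.2% |
| .4 | 84% | 72.8% |
| .5 | 75% | 67.9% |

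**Several predictors.** Let b be the vector of true coefficients, g the coefficients of B on the predictors jointly, and h the slope of each predictor on B. Then b_res = b − g(h′b). Two things follow. A term is distorted only if its own element of g is nonzero. The direction depends on the sum h′b, so contributions can cancel.

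**Simulation.** N = 200, 4,000 replicates, equal allocation, slope on the comparison value 0.6; all effects and correlations are assumed.

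| Scenario | Term | Single model | Residual |
|---|---|---|---|
| Puberty alone related to B (r about −.3) | puberty | 0.160 (power 74%) | 0.147 (71%) |
| | parent | 0.381 | 0.380 |
| Puberty and sex related to B (−.24, .18), effects aligned with those correlations | puberty | −0.161 (75%) | −0.141 (68%) |
| | sex | 0.331 (77%) | 0.298 (72%) |
| Same correlations, puberty effect reversed | puberty | 0.160 | 0.157 |
| | sex | 0.330 | 0.333 |
| Parent presence also lowers B by 0.5 | parent | −0.379 | −0.363 |
| | puberty | 0.160 | 0.168 |
| B unaffected by condition | parent × puberty | 0.379 | 0.377 |
| B shifted by condition and by condition × puberty | parent × puberty | 0.383 | 0.366 |

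With a true puberty effect of zero and a real sex effect, the residual method rejected for puberty 4.5% of the time, so there was no false-positive inflation in that case.

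**If condition moves the comparison value.** In the fourth scenario the direct parent effect is −0.38 and B is lowered by 0.5, so the total effect on the stress value is −0.38 + 0.6 × (−0.5) = −0.68. The single model returns −0.379 and the residual method −0.363. Neither estimates the total effect, and that gap is far larger than the gap between the two methods.

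**Which comparison period?** None is named for heart rate or respiration. Section 15.1 uses the resting scan as comparison for connectivity and math without judges for activation. Under Stressor Paradigm (section 5.2) both lie inside the scan, and math without judges comes after the judged math. The parent link runs for the scan's duration, but the resting scan is described as free of video and audio. Whether the child is exposed to the social partner during rest cannot be settled from the text.

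**The case against.** The best case for leaving the plan alone is that the hypothesis of interest is hardly touched. Hypothesis 1 says that buffering wanes with puberty, which is the condition × puberty term. Section 15.3 tests the three-way term first and reaches main-effects models only if the interactions are not significant. A reader might infer that puberty's role as moderator is the part most at risk. The documents and the algebra do not support that. With a comparison value unaffected by condition, the interaction is essentially unchanged (0.379 against 0.377), and it stays so even at a puberty correlation of .5 (0.382 against 0.380). It moves only when the comparison value itself shifts by condition × puberty. This part of the objection stands.

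Two further limits also stand. The correlation r is given nowhere, so a 25% loss illustrates one assumed value and is not a forecast. Shrinkage is also not certain with puberty and sex both in the model: the table shows one case with almost no change and one where the puberty coefficient rises.

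A reader might also infer that the comparison value is definitely measured after exposure. The plan says that the parent is connected to staff throughout, not that the child sees or hears the parent during rest, so this remains possible but unproven.

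None of this defends the residual step. When r is zero, the two methods estimate the same coefficient; otherwise the residual method generally does not recover the adjusted effect.

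**Conclusion.** The point holds in a limited form. The two-step residual is the stated method, the comparison value is absent from the second model, and the coefficient of a predictor related to the comparison value is distorted, usually toward zero. With one such predictor the loss is 1% to 9% for r = .1 to .3 and 25% for r = .5, with r assumed.

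The main effects of puberty and sex are the most exposed. The condition effect is affected only if condition shifts the comparison value, and the condition × puberty term only if that shift varies with puberty. The documents do not support a claim that the test of Hypothesis 1 is generally biased, or that puberty and sex effects must shrink.

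The unnamed comparison period matters as much as the residual step, because it decides what the adjusted condition effect means. For respiration the second-stage model is not written at all, so the concern there is that the same construction would carry over.

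**What to change.** 1. Drop the residual step. In the section 15.3 models use the stress-period heart rate as the outcome and enter the comparison-period value as a covariate in the same model, fixed in advance and not subject to the section 15.1 screen.
2. Name the comparison period for these signals and state whether it precedes the start of the social-partner manipulation. Use a pre-manipulation value where one exists.
3. If none exists, state that the adjusted condition effect is conditional on a post-exposure value, and also report the condition effect on the stress-period value without that adjustment.
4. Name respiration in section 15.3 and apply the same model to it.

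The cost is one degree of freedom: v goes from 176 to 175 and the minimum detectable f² from 0.0548 to 0.0551. No new data are needed. Beyond the wording, the sponsor has to decide on the comparison period and establish its timing relative to the manipulation.

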## **6.0 Data and Specimen Banking**

**6.1 Storage and Access:** Saliva samples will be stored in a -20 degree freezer until they can be batched with other samples for hormonal assay. Any material remaining after the planned assays will be discarded. No tissue or biological samples will be stored for future use or shared.

Biospecimen samples will be identified only with a unique study ID, child age, child sex, and sample number. No PHI will be associated with any biospecimen samples. Samples will not identify the study condition of interest (i.e., social buffering condition).

**6.2 Sharing:** De-identified data will be shared with qualified researchers when requested for scientific purposes including replication of results, use in meta-analyses, or appropriate extension of analyses. No biospecimen samples will be saved or shared.

## **7.0 Sharing of Results with Participants**

**7.1** Results will only be shared with participants in aggregate, with the following exceptions:

We will take anthropomorphic measures (such as height and weight) as well as pubertal staging and these figures will be shared with parents at the time of the session. We deliver the figures on a post-card, with links to national pediatric norms provided by the CDC.

Regarding other hormonal or physiological measures in this study, abnormal values are commonly due to an interfering substance present in the sample (e.g., milk for salivary cortisol) or motion artifact in the case of EKG. Without a body of evidence, it seems unethical to alarm families given an out-of-range assay value and therefore we do not plan to share individual results with participant.

In the event that the scanner operator or study personnel see something unusual in the MRI scan, the images will be submitted for review by a radiologist. Images contain only the study ID number, participant's age in years, participant sex, and test date. In the event that the radiologist determines that the incidental finding should receive clinical follow-up, we will share this information with the parent(s) of the minor child participant with the recommendation to consult with the child's primary care physician. Incidental findings from research scans are not clinically diagnostic and the images may not be added to the child's medical record.

## **8.0 Study Population**

- 8.1 Inclusion Criteria: Healthy 11- to 14-year-olds. Additional inclusion criteria ensure that youth will be able to follow the study procedures (have sufficient vision, hearing, and language skills to provide verbal and written assent, see and read stimuli presented on the computer screen, and hear verbal instructions provided by the experimenter and/or judges).
- 8.2 Exclusion Criteria for child participation: Premature birth (less than 37 weeks), congenital and/or chromosomal disorders (e.g. cerebral palsy, FAS, mental retardation, Turner Syndrome, Down Syndrome, Fragile X), Autism Spectrum Disorders, history of serious medical illness (e.g., cancer, organ transplant), youth using systemic glucocorticoids or beta-adrenergic medications, diagnosed psychiatric illness or psychotropic medication, seizure disorder or other neurological disorder, academic delay or individualized education plan (IEP), contraindications for MRI (implanted medical device; presence of non-removal metal in or on the body, including piercings, orthodontic braces or certain permanent retainers), known pregnancy, tattoo, or history of significant claustrophobia.
- 8.3 Screening: Screening will occur by asking parents questions at the time of telephone recruitment. To reduce confounding of age and pubertal stage, we will use a stratified recruitment method. During recruitment, parents will be asked 3 questions about their child's physical development, and children will be initially categorized into Pre/Early and Mid/Late Puberty. As

cells fill, participants will no longer be enrolled into those cells. Also, to increase minority representation we will sample across zip codes with higher racial and ethnic minority representation.

## 9.0 Vulnerable Populations

### 9.1 Vulnerable Populations:

Population / Group	Identify whether any of the following populations will be targeted, included (not necessarily targeted) or excluded from participation in the study.
Children	Targeted Population
Pregnant women/fetuses/neonates	Excluded from Participation
Prisoners	Excluded from Participation
Adults lacking capacity to consent and/or adults with diminished capacity to consent, including, but not limited to, those with acute medical conditions, psychiatric disorders, neurologic disorders, developmental disorders, and behavioral disorders	Excluded from Participation
Non-English speakers	Excluded from Participation
Those unable to read (illiterate)	Excluded from Participation
Employees of the researcher	Excluded from Participation
Students of the researcher	Excluded from Participation
Undervalued or disenfranchised social group	Included/Allowed to Participate
Active members of the military (service members), DoD personnel (including civilian employees)	Included/Allowed to Participate
Individual or group that is approached for participation in	Excluded from Participation

research during a stressful situation such as emergency room setting, childbirth (labor), etc.	
Individual or group that is disadvantaged in the distribution of social goods and services such as income, housing, or healthcare.	Included/Allowed to Participate
Individual or group with a serious health condition for which there are no satisfactory standard treatments.	Excluded from Participation
Individual or group with a fear of negative consequences for not participating in the research (e.g. institutionalization, deportation, disclosure of stigmatizing behavior).	Included/Allowed to Participate
Any other circumstance/dynamic that could increase vulnerability to coercion or exploitation that might influence consent to research or decision to continue in research.	Excluded from Participation

